2.2. Endpoints

Primary efficacy endpoint

- Time to sustained withdrawal of supplementary oxygen (11-category WHO Clinical Progression Scale ≤ 4) with no subsequent reutilisation during remaining study period (See [Appendix 13 - World Health Organization \(WHO\) Clinical Progression Scale](#)).

Key secondary efficacy endpoint

- Time to sustained (i.e., with no subsequent readmission to Day 31) hospital discharge (since randomisation).

Secondary endpoints

Efficacy:

- Clinical status, as assessed by the 11 category WHO Clinical Progression Scale, at Day 8 (± 1) (See [Appendix 13 - World Health Organization \(WHO\) Clinical Progression Scale](#)).
- Total duration of advanced oxygen support (high-flow nasal oxygen, extracorporeal membrane oxygenation -ECMO-, non-invasive ventilation or mechanical ventilation).
- Percentage of patients in each study group requiring admission to ICU on Days 4, 8, 15, and 31.

Safety/tolerability:

- Frequency of TEAEs;
- Frequency of TEAEs of ≥ 3 according to NCI-CTCAE v5.0;
- Frequency of treatment-emergent adverse events of special interest (AESIs);
- Frequency of serious adverse events (SAEs);
- Frequency of drug-related serious adverse events (i.e., SARs);
- Frequency of adverse events leading to treatment discontinuation;
- Frequency of deaths;
- Change respect to baseline in individual study-defined laboratory parameters (See [Section 7.2.4.](#));
- Change respect to baseline in individual vital signs (See [Section 7.2.5.](#));
- Change respect to baseline in individual study-defined ECG parameters (See [Section 7.2.5.](#)).

Other secondary endpoints

- Percentage of patients in each study group requiring hospital readmission due to COVID-19-related signs or symptoms through Day 31.

- Percentage of patients in each study group and in each of the categories of the 11-category WHO Clinical Progression Scale on Days 4, 8, 15 and 31 (See [Appendix 13 - World Health Organization \(WHO\) Clinical Progression Scale](#)).
- Percentage of patients in each study group requiring oxygen therapy on Days 4, 8, 15 and 31.
- Time to intensification of respiratory support (WHO >6 [intubation]) (See [Appendix 13 - World Health Organization \(WHO\) Clinical Progression Scale](#)).
- Total duration of intensive care unit (UCI) stay for each study group.
- Percentage of patients in each study group requiring high-flow oxygen on Days 4, 8, 15, and 31.

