3. INVESTIGATION PLAN

3.1. Overall Study Design and Plan Description

An overview of study design is shown in [Figure 1](#). This is a multicentre, open-label, controlled Phase 3 study in which adults requiring hospital admission and O₂ supplementation for management of moderate COVID-19 infection will be randomised in 1:1:1 to:

- Plitidepsin 1.5 mg arm: Patients will receive plitidepsin 1.5 mg/day intravenous (IV) in addition to dexamethasone on days 1 to 3 ([See Section 5. Study treatments](#)).
- Plitidepsin 2.5 mg arm: Patients will receive plitidepsin 2.5 mg/day IV in addition to dexamethasone on days 1 to 3 ([See Section 5. Study treatments](#)).
- Control arm: Patients will receive dexamethasone IV on Days 1 to 3. Additionally, in accordance with local treatment guidelines, patients in this group may receive a regulatory-approved antiviral treatment ([See Section 5. Study treatments](#)).

Randomisation will be stratified for 3 factors:

- a) Geographical Region (Europe *versus* Rest of the World);
- b) Charlson Comorbidity Index (0-1 *versus* >1) ([Appendix 11 – Age-adjusted Charlson Index](#)); and
- c) Barthel Index (≥ 90 *versus* <90) ([Appendix 7 - Barthel Index for Functional Assessment](#)).

[figure not shown]
From treatment initiation on Day 1, patients will be followed in the hospital for at least 4 days and then through Day 31 (± 3 days) or resolution/stabilisation of treatment-related adverse events, treatment-emergent adverse events of special interest, and SAEs. Patients discharged from the hospital prior to Day 8 will return to an out-patient clinic for assessments on Days 8 (± 1 day) and 31 (± 3 days). On Day 15 (± 1 day), patients will be followed up in remote or on-site visit ([Appendix 5 – Schedule of Assessments](#)).

An Independent Data Monitoring Committee (IDMC) will oversee study conduct (safety and primary endpoint), including analysis of summary safety data as per the trial requirements.

The study is expected to randomise approximately 609 patients (203 in each arm) over a period of 20 months.

Patients will be considered to be on study from the signature of the informed consent form (ICF) until the end of the follow-up period, that is, completion of the protocol-specified follow-up visit on Day 31 (± 3 days) or until resolution/stabilisation of treatment-related AEs, treatment-emergent adverse events of special interest, and SAEs that occurred through Day 31, whichever is longer.

Figure 1. Schema of the Study

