7.1. Efficacy Assessments

7.1.1. Test for COVID-19

Quantitative PCR to assess viral load on Day 1 before initiation of treatment and on Day 8 (± 1 day) (see Schedule of Assessments [[Appendix 5](#)]), will be performed by a central laboratory. Based on these assessments, changes in viral load from Day 1 to Day 8 will be calculated for each patient. The proportion of patients with undetectable SARS-CoV-2 on Day 8 will also be assessed.

Details regarding the collection, processing, storage, and shipment of oro-nasopharyngeal samples for qPCR testing will be provided to each investigational site before initiation of the study in the form of a laboratory manual. All oro-nasopharyngeal samples for qPCR must be processed and shipped as specified in the laboratory manual to maintain sample integrity. Any deviations from the processing steps (e.g., sample collection and processing steps, interim storage, or shipping conditions), including any actions taken, must be documented and reported to the sponsor. On a case-by-case basis, the sponsor may make a determination as to whether sample integrity has been compromised. Any deviation from the specified sample handling procedure that results in compromised sample integrity will be considered a protocol deviation.

Samples will be analysed using validated analytical methods, as approved by the sponsor.

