- TriPLICATE 12-lead ECG to assess QTcF interval (*Day 31 only and at end of study visit*).

- Haematology (RBC, haemoglobin, haematocrit, WBC with differential, platelet count).
- Coagulation (D-dimer).
- Serum chemistry (ALT, AST, alkaline phosphatase, GGT, LDH, total bilirubin, direct bilirubin, glucose [fasting], sodium, potassium, calcium (albumin adjusted calculation), magnesium, BUN, creatinine, calculated creatinine clearance [Cockcroft-Gault equation], CPK, troponin T [high sensitivity], NT-pro-BNP, albumin, amylase, lipase, and procalcitonin).
- Immunology (CRP, ferritin, IL-1 β , IL-6, IL-10, and TNF α).
- Quantitative PCR for COVID-19 viral load (*Day 8 only*).
- Serological SARS-CoV-2 testing (IgG) (*Day 31 only and at end of study visit*).
- Chest imaging (using same technique as baseline).
- Concomitant medications.
- Adverse events/TEAEs.
- Functional status using the Barthel index ([Appendix 7](#)) score.
- Clinical status, using the 11-point WHO Clinical Progression Scale (highest category that applies) ([Appendix 13](#)).
- Administration of dexamethasone base will be continued at 6 mg/day PO/IV (equivalent to 7.2 mg dexamethasone phosphate) up to a total cumulative dose of 60 mg, per physician judgement based on patient clinical condition and evolution.

7.4.2.4. Day 15

The following assessments will be performed on Day 15 (± 1), in remote or on-site visit:

- Concomitant medications.
- Adverse events/TEAEs.
- Functional status, using the Barthel index ([Appendix 7](#)) score.
- Clinical status, using the 11-point WHO Clinical Progression Scale (highest category that applies) ([Appendix 13](#)).

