8.5.3. Other Secondary Efficacy Outcome Measures

Descriptive statistics for the other secondary efficacy endpoints will be presented by treatment group and by study visit where appropriate. We will use similar methods as specified for the analyses of the primary and secondary variables.

For binary endpoints, the treatment group comparisons will be performed at Day 8 (± 1 day) only, with descriptive statistics provided for each clinic visit.

Longitudinal analyses will be also performed assuming mixed-effect models including treatment effect, time effect, randomisation stratification factor and a time-treatment interaction as covariates, using a covariance structure of autoregressive order 1.

The clinical status, as assessed on the 11-point WHO Clinical Progression Scale ([Appendix 13](#)) on Day 8 (± 1 day), will be summarised by treatment group. The clinical status at Day 8 (± 1 day) between each dose of plitidepsin *versus* control arm will be compared using a proportional odds model. The model will be adjusted for the randomisation stratification factors. The odds ratios, 2-sided 95% CIs, and p-values for the comparison of each dose of plitidepsin *versus* control arm will be presented.

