- 7 Coagulation:** D-dimer
- 8 Immunology:** Proinflammatory biomarkers (CRP, ferritin, IL-1 β , IL-6, IL-10, TNF α) in each study arm from baseline (Day 1 prior to start of the study treatment) to Day 4 and Days 8 (± 1 day), 15 (± 1 day) and 31 (± 3 days).
- 9 COVID-19 screen:** Qualitative PCR, antigen test to be performed by local laboratory, or any other validated method approved by the local health authority, from appropriate biological samples collected no more than 72 hours before study treatment on Day 1 for screening test to confirm COVID-19. In case more than one is available, the more recent one will be selected.
- 10 COVID-19 viral load:** Quantitative real-time reverse transcription polymerase-chain-reaction test (qRT-PCR) test to be performed by central laboratory from oro-nasopharyngeal exudate on Day 1 prior to initiating treatment and on Day 8 (± 1 day).
- 11 Chest imaging:** CT scan or x-ray will be done on Days 1, 8 (± 1 day) and 31 (± 3 days), Chest imaging performed within 48 hours of Day 1 is accepted and does not have to be repeated
- 12 Pregnancy test:** Serum or urine pregnancy test for females of child-bearing potential, to be performed by local laboratory for screening
- 13 Clinical Status:** Assessed using the 11-point WHO Clinical Progression Scale ([Appendix 13](#)) will be performed at screening, daily from Day 1 while hospitalised and on Days 8 (± 1 day), 15 (± 1 day) and 31 (± 3 days), where 0 = uninfected, no viral RNA detected; 1 = asymptomatic, viral RNA detected; 2 = symptomatic, independent; 3 = symptomatic, assistance needed; 4 = hospitalised, no oxygen therapy (if hospitalised for isolation only, record status as for ambulatory patient); 5 = hospitalised, oxygen by mask or nasal prongs; 6 = hospitalised, oxygen by NIV or high flow; 7 = intubation and mechanical ventilation, pO₂/FIO₂ ≥ 150 or SpO₂/FIO₂ ≥ 200 ; 8 = mechanical ventilation, pO₂/FIO₂ < 150 (SpO₂/FIO₂ < 200) or vasopressors; 9 = mechanical ventilation, pO₂/FIO₂ < 150 and vasopressors, dialysis or ECMO; 10 = dead.
- 14 Functional Status:** Assessed by the Barthel index score ([Appendix 7](#)); the pre-baseline (i.e., > 1 month prior to screening) functional status should be recorded, in addition to Day 1 prior to initiating study treatment, at hospital discharge, and on Days 8 (± 1 day), 15 (± 1 day) and 31 (± 3 days).

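### WHO scores 0 and 1 differ only by a viral RNA result, but no RNA test is scheduled on Days 15 and 31, where both categories are reported, and the Day 8 score is not linked to the central PCR

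*Protocol*

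**What the plan says.** **Scale.** Appendix 5, footnote 13, gives the two lowest scores as "0 = uninfected, no viral RNA detected; 1 = asymptomatic, viral RNA detected". Appendix 13 says the same. Scores 2 and 3 depend on symptoms and need for assistance, not on RNA.

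**RNA testing.** Section 7.1.1 plans "Quantitative PCR to assess viral load on Day 1 before initiation of treatment and on Day 8". Appendix 5, footnote 10, has it "performed by central laboratory from oro-nasopharyngeal exudate on Day 1 prior to initiating treatment and on Day 8". A qualitative PCR, antigen or other validated test at screening confirms eligibility.

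**Visits.** For Day 15, Section 7.4.2 says "The following assessments will be performed on Day 15 (± 1), in remote or on-site visit". The list that follows includes clinical status but no PCR. The joint Day 8 and Day 31 list restricts the viral load PCR to Day 8.

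**Use of the scale.** An other secondary endpoint in Section 2.2 is the percentage of patients "in each of the categories of the 11-category WHO Clinical Progression Scale on Days 4, 8, 15 and 31". Day 8 clinical status is a secondary endpoint. Under Section 8.5.3, each dose and control "will be compared using a proportional odds model".

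**The concern.** The scoring rule needs a laboratory result that the assessment schedule does not supply on two of the four reporting days. Appendix 13 gives an asymptomatic patient seen on Day 15 or Day 31 a 0 or a 1, and nothing collected under the schedule says which. The tables would then show two separate percentages whose split rests on no scheduled data.

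On Day 8 the result will exist, but it comes from a central laboratory after the swab is shipped, while clinical status is scored at the visit. No section says that the score waits for the result or is revised by it. If the visit score is analysed as recorded, the 0/1 split in the proportional-odds model is whatever the site entered, in a trial where the site knows the arm.

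**Working it through.** **1. Schedule against endpoint days**

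| Day | Score reported | RNA test scheduled | Can 0 and 1 be separated? |
|---|---|---|---|
| 4 | yes | no | rarely arises |
| 8 | yes, and modelled | yes, central | yes, if the result is used |
| 15 | yes (visit may be remote) | no | no |
| 31 | yes | no | no |

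Day 4 is nearly moot because Section 3.1 states that "patients will be followed in the hospital for at least 4 days", so patients score 4 or more. The exception is the Appendix 13 footnote, which scores a patient hospitalised only for isolation as ambulatory.

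**2. Does another rule settle it?** Section 7.4.2 asks for the highest category that applies. Score 1 requires RNA detected and score 0 requires none detected; without a result, neither can be shown to apply. Clearance cannot be presumed either: Table 3 gives a mean time to undetectable viral load of 13 days in the earlier plitidepsin study, so RNA status is still changing around these visits.

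**3. How many patients?** Take discharge shares from Table 3 and assume they carry over. Day 15: 36/44 = 81.8%, and 0.818 × 609 ≈ 498 patients. Day 31: 40/44 = 90.9%, and 0.909 × 609 ≈ 554. These are upper bounds, since only asymptomatic patients face the choice. The protocol does not give that share. At an assumed 30% to 70%, the affected fraction is 25% to 57% on Day 15 and 27% to 64% on Day 31.

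**4. Primary and key secondary.** The primary endpoint cuts the scale at 4 or lower, so 0 and 1 fall on the same side. Time to sustained discharge does not use the scale. Effect on both: none.

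**5. Day 8, if site scores are used and differ by arm.** Assume no true effect and 203 per arm. Let b be the share of each arm that is asymptomatic, and let a (control) and c (plitidepsin) be the probabilities that such a patient is scored 0.

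- Spurious net probability of a better score: b²(c − a).
- Rank-test standard error: 2√[(N + 1)(1 − Σp³)/(12n²)], with N = 406, n = 203 and p the pooled category shares.
- Two-sided error: Φ(−1.96 + z) + Φ(−1.96 − z), with z the ratio of the two.

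All scoring rates are assumptions: a = 0.30, c = 0.50 or 0.70. Two layouts are used. One has 57% ambulatory, the earlier study's discharge share by Day 8. The other has 42% ambulatory, 8% at score 4 and 50% at score 5 or higher, matching the 8-day control median in Section 8.1. In both, score 4 holds 8%, and scores 5, 6, 7–9 and 10 share the remainder in the ratio 25:6:3:1 (assumed). Scores 2 and 3 are one group.

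| Ambulatory | Asymptomatic among them | b | Error, c = 0.50 | Error, c = 0.70 |
|---|---|---|---|---|
| 57% | 30% | 0.171 | 5.1% | 5.5% |
| 57% | 50% | 0.285 | 6.0% | 8.9% |
| 57% | 70% | 0.399 | 8.7% | 20.5% |
| 42% | 30% | 0.126 | 5.0% | 5.2% |
| 42% | 50% | 0.210 | 5.3% | 6.2% |
| 42% | 70% | 0.294 | 6.1% | 9.5% |

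Example, last cell: b = 0.42 × 0.70 = 0.294; b²(c − a) = 0.0864 × 0.40 = 0.0346; SE = 0.0558; z = 0.62; error 9.5%.

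Simulating the 42% layout (2,000 runs) gave odds ratios of 1.01 to 1.06 in five of the six cases and 1.12 in the last, with error 9.9%. If c = a the term vanishes and the error is 5%. If 0 and 1 are merged, it vanishes whatever a and c are.

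**The case against.** The strongest reply is that this is a descriptive detail. Category percentages on Days 15 and 31 are an other secondary endpoint. The only model named for the full scale is on Day 8, where a PCR is scheduled. Section 8 defers specifics to the SAP, which could merge categories or define how the central result feeds the score. Unscheduled local testing is not forbidden.

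Much of this stands. It limits the weight of the point and leaves Day 8 as a missing link rather than missing data. It does not remove the mismatch on Days 15 and 31: the endpoint and the schedule are both fixed in the protocol, and an SAP cannot recover RNA results that were never collected.

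A reader might infer three stronger things that the protocol does not support:

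- **That recovered patients cannot be scored.** Only 0 versus 1 is open. That the patient is below 2 is known, and scores 2 and 3 need no RNA result.
- **That unblinded sites guess in favour of plitidepsin.** The trial is open-label, but no section says sites guess, and nothing shows that scoring differs by arm. The rates used above are assumptions.
- **That the Day 8 test is materially biased.** The larger errors need the 57% layout or the extreme rates. The 57% comes from an all-plitidepsin study that included mild disease, whereas this trial enrols only patients on oxygen and assumes a control median of 8 days to sustained withdrawal.

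**Conclusion.** The mismatch is real and minor. On Days 15 and 31, and on Day 4 only for patients held for isolation, an asymptomatic patient cannot be given 0 or 1 from scheduled data, although both percentages are to be reported. On Day 8 the result exists, but the protocol does not connect it to the score.

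The share affected on Days 15 and 31 depends on the unknown asymptomatic fraction and on discharge shares borrowed from the earlier study. The primary and key secondary endpoints are untouched. Bias by arm on Day 8 is possible but not shown. With the protocol's own control median and the assumed differential scoring, the two-sided error stays at about 5% to 6% in five of six cases and reaches about 10% only in the extreme one.

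**What to change.** In Sections 2.2 and 8.5.3:

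- Report scores 0 and 1 as one category, *ambulatory, asymptomatic*, in the category tables on Days 4, 15 and 31 and in any longitudinal analysis of the scale.
- For the Day 8 table and proportional-odds model, either use the same merged category or derive 0 versus 1 from the central Day 8 qPCR, not from the site's score at the visit.
- Keep undetectable viral load on Day 8 as its own endpoint, as already planned.

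This changes wording only and adds no test. The cost is one category fewer at the recovered end of the scale. On Days 15 and 31 the split had no scheduled data behind it. On Day 8, merging would give up a distinction that the central qPCR can supply, which is why deriving it from that result is offered as the alternative.

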Appendix 6 - Contraception and Pregnancy Testing

This document is based on the Heads of Medicines Agencies' Recommendations Related to Contraception and Pregnancy Testing in Clinical Trials, published by the Clinical Trial Facilitation Group (CTFG) on 21 September 2020 and available at https://urldefense.com/v3/_https://www.hma.eu/fileadmin/dateien/Human_Medicines/01-About_HMA/Working_Groups/CTFG/2020_09_HMA_CTFG_Contraception_guidance_Version_1.1_updated.pdf

A woman is considered of child-bearing potential (WOCBP) following menarche and until becoming postmenopausal unless permanently sterile. Permanent sterilisation methods include hysterectomy, bilateral salpingectomy and bilateral oophorectomy. A postmenopausal state is defined as no menses for 12 months without an alternative medical cause. A high follicle stimulating hormone (FSH) level in the postmenopausal range may be used to confirm a postmenopausal state in women not using hormonal contraception or hormonal replacement therapy. However, in the absence of 12 months of amenorrhoea, a single FSH measurement is insufficient. Immediately after detecting a case of suspected pregnancy in a patient, the decision on her continued participation in the clinical trial will be jointly taken by the patient, the Investigator and the Sponsor, with the patient's best interest in mind. A decision to continue the pregnancy will require immediate discontinuation of any investigational medicinal product (IMP).

A man is considered fertile after puberty unless permanently sterile by bilateral orchidectomy. Fertile male patients included in this study should refrain from fathering a child or donating sperm during the study and for 6 months following the last IMP dose. If they have WOCBP partners the male subject should use condom during treatment and for 6 months following the last IMP dose.

Highly effective birth control methods are:

1. Combined (oestrogen and progestogen containing) hormonal contraception associated with inhibition of ovulation¹:
 - a. oral
 - b. intravaginal
 - c. transdermal
2. Progestogen-only hormonal contraception associated with inhibition of ovulation¹:
 - a. oral
 - b. injectable
 - c. implantable²
3. Intrauterine device (IUD)²
4. Intrauterine hormone-releasing system (IUS)²
5. Bilateral tubal occlusion²
6. Vasectomised partner^{2,3}
7. Sexual abstinence⁴
8. A combination of male condom with either cap, diaphragm, or sponge with spermicide (double barrier methods) are also considered acceptable, but not highly effective, birth control methods.

¹ Hormonal contraception may be susceptible to interaction with the IMP, which may reduce the efficacy of the contraception method (see below).

² Contraception methods that are considered to have low user dependency.

³ Vasectomised partner is a highly effective birth control method provided that partner is the sole sexual partner of the WOCBP trial participant and that the vasectomised partner has received medical assessment of the surgical success.

⁴ Sexual abstinence is considered a highly effective method only if defined as refraining from heterosexual intercourse during the entire period of risk associated with the study treatments. The reliability of sexual abstinence needs to be evaluated in relation to the duration of the clinical trial and the preferred and usual lifestyle of the subject. Periodic abstinence (calendar, symptothermal, postovulation methods), withdrawal (coitus interruptus), spermicides only, and lactational amenorrhoea method (LAM) are not acceptable methods of contraception. Female condom and male condom should not be used together.

Contraception methods with low user dependency should preferably be used, in particular when contraception is introduced as a result of participation in this trial.

Appendix 7 – Barthel Index for Functional Assessment

	With help	Independent
1. Feeding (if food needs to be cut = help)	5	10
2. Moving from wheelchair to bed and return (includes sitting up in bed)	5-10	15
3. Personal toilet (wash face, comb hair, shave, clean teeth)	0	5
4. Getting on and off toilet (handling clothes, wipe, flush)	5	10
5. Bathing self	0	5
6. Walking on level surface (or if unable to walk, propel wheelchair)	10 0*	15 5*
*score only if unable to walk		
7. Ascend and descend stairs	5	10
8. Dressing (includes tying shoes, fastening fasteners)	5	10
9. Controlling bowels	5	10
10. Controlling bladder	5	10

